## 4 STUDY POPULATION

### 4.1 Population Base

At least 12 paediatric subjects with clinically diagnosed congenital fibrinogen deficiency (i.e., afibrinogenaemia or severe hypofibrinogenaemia) will be enrolled into the study and undergo PK assessment. Of these 12 subjects, at least 6 subjects will undergo on-demand treatment of 6 first bleeding episodes. Of these 6 subjects, at least 3 should be aged between 0 and <6 years and 3 should be aged between 6 and <12 years.

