### 4.2 Inclusion Criteria

Subjects who meet all of the following criteria are eligible for the study:

1. Aged <12 years (at the start of treatment)
2. Documented diagnosis of congenital fibrinogen deficiency, expected to require on-demand treatment for bleeding or surgical prophylaxis:
  - Fibrinogen deficiency manifested as afibrinogenaemia or severe hypofibrinogenaemia
  - Historical plasma fibrinogen activity of <50 mg/dL or levels below the limit of detection of the local assay method
3. Expected to have an acute bleeding episode (spontaneous or after trauma) or planning to undergo elective surgery.
4. Informed consent signed by the subject's legal guardian

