### Subpopulations

Subpopulations based on the following categories will be examined:

- Severity of bleeding: minor versus major (subpopulations of the BLEED analysis set)
- Age 0 to <6 years versus 6 to <12 years (subpopulations of the BLEED-PP and the SURG-PP analysis set)

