### **7.7 Statistical Analytical Issues**

The statistical analysis of the primary, secondary and safety endpoints is to be understood in the exploratory sense. Therefore no confirmative statistical analysis is planned.

Subgroup analyses are planned for the two age strata (age groups < 6 years and  $\geq 6$  - 12 years) regarding PK results, in treatment of BEs and in surgical procedures as well as regarding adverse events.

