## 10 EVALUATION OF TREATMENT EFFICACY

The primary endpoint is the overall clinical assessment of haemostatic efficacy of *Octafibrin* in treating the first documented bleeding episode of each patient (FirstBLEED population).

The efficacy will be evaluated by descriptive statistics and all results will be presented stratified by the age groups (2-<6 years, 6-12 years), if appropriate, and in total. The stratification will be done according to the age of the patients at the screening assessment and patients will stay in the respective stratum for all analyses even when the age of the patient crosses the border of the first stratum.

Secondary endpoints are the clot strength after treatment of a bleeding episode with *Octafibrin*, the in-vivo recovery, the efficacy of *Octafibrin* in all bleeding episodes, and the surgical prophylaxis.

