## 10.5 Surgical Prophylaxis

Efficacy of *Octafibrin* in surgical prophylaxis will be assessed intra-operatively (at the end of surgery = after last suture) by the surgeon and post-operatively (at the last post-operative day) by the haematologist using two 4-point efficacy scales.

The primary analysis regarding haemostatic efficacy will be done on the adjudicated assessments by the algorithm described above and by the IDMEAC.

The following will be presented in frequency tables with descriptive statistics or in listings, depending on the number of surgeries:

- Number of subjects undergoing surgeries (minor, major, total)
- Number of surgeries, overall (minor, major, total)
- Surgery characteristics (type and site, pre-planned (yes/no), severity, expected and actual duration, expected and actual blood loss) will be listed.
- Details on treatment for surgical prophylaxis (number of exposure days and injections prior to surgery, dosing details, total amount of *Octafibrin*) will be listed.
- Pre-, intra-, and post-operative fibrinogen plasma levels, pre- and post-infusion will be listed.
- Efficacy evaluation by the surgeon at the end of the surgery and by the haematologist on the last post-operative day.
- Subjects who switch to another FIX product during a surgery will be considered treatment failures, i.e. the efficacy will be imputed to be “none” for each haemostatic efficacy assessment after the switch in the efficacy analyses for this surgery.
- Adjudicated overall efficacy assessment of the surgeries using the algorithm for the adjudicated intra- and post-operative assessments of haemostatic efficacy (as described in chapter 3.3.6 of this SAP). All assessments adjudicated by the IDMEAC will be listed together with the surgery details and the intra- and post-operative assessments of the surgeon and the haematologist.

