14.2.3	T	Frequency of bleeding episodes per age group and in total	BLEED, BLEED-PP (age groups)
14.2.4	T	First bleeding episode per type of BE (spontaneous, traumatic, post-operative, other)	BLEED, BLEED-PP
14.2.5	T	Bleeding episodes per type of BE (spontaneous, traumatic, post-operative, other)	BLEED, BLEED-PP
14.2.6	T	Site of first bleeding episode	BLEED, BLEED-PP
14.2.7	T	Site of bleeding episodes	BLEED, BLEED-PP
14.2.8	T	Treatment duration of the first bleeding episode	BLEED, BLEED-PP
14.2.9	T	Treatment duration of bleeding episodes	BLEED, BLEED-PP
14.2.10	T	Severity of first bleeding episode (mild, moderate, severe)	BLEED, BLEED-PP
14.2.11	T	Severity of bleeding episodes (mild, moderate, severe)	BLEED, BLEED-PP
14.2.12	T	Efficacy assessment (final outcome) of treatment of first bleeding episode a) Four point scale (14.2.11.1) (excellent, good, moderate, none) b) Two point scale (successfully treated (excellent or good), not successfully treated (moderate or none) (14.2.11.2))	BLEED, BLEED-PP (age groups)
14.2.13	T	Statistics on successfully treated first bleeding episodes (two-sided 95% Clopper-Pearson confidence interval)	BLEED, BLEED-PP
14.2.14	T	Efficacy assessment (final outcome) of treatment of bleeding episodes a) Four point scale (14.2.13.1) (excellent, good, moderate, none) b) Two point scale (successfully treated (excellent or good), not successfully treated (moderate or none) (14.2.13.2))	BLEED, BLEED-PP (age groups)
14.2.15	L	Treatment details for each bleeding episode per patient (incl. exposure days, number of injections, dosing inc. batch numbers, consumption of Octafibrin, haemostatic co-medication)	BLEED, BLEED-PP
14.2.16	T	Statistics on successfully treated bleeding episodes (two-sided 95% Clopper-Pearson confidence interval)	BLEED, BLEED-PP
14.2.17	T	Statistics on MCF and fibrinogen activity for samples taken before and 1 hour after the end of the first infusion (including confidence interval for the difference)	BLEED, BLEED-PP
14.2.18	T	Statistics on MCF and fibrinogen activity for samples taken before and 1 hour after the end of the first infusion separated by four/two point efficacy scale	BLEED, BLEED-PP
14.2.19	F	Boxplot MCF and fibrinogen activity for samples taken before and 1 hour after the end of the first infusion separated by four/two point efficacy scale	BLEED, BLEED-PP
14.2.20	T	Statistics on final efficacy assessment of the IDMEAC and the efficacy assessment of the investigator	BLEED, BLEED-PP

		Surgeries	

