14.3.2	T	Summary of Adverse Events number of subjects with any AE, SAE, Severe AE or possibly or probably related AE, AEs that begin within 24 hours of end of infusion	SAF
14.3.3	T	Number of subjects with treatment-emergent adverse events by system organ class and preferred term – SAF	SAF
14.3.4	T	Number of subjects with treatment-emergent possibly/probably related to study drug by system organ class and preferred term – SAF	SAF
14.3.5	T	Number of subjects with treatment-emergent adverse events temporally related (within 24 hours after end of infusion) to study drug by system organ class and preferred term - SAF	SAF
14.3.6	T	Number of subjects with treatment-emergent adverse events by severity by system organ class and preferred term – SAF	SAF

14.3.7	T	Summary of adverse events by age group (2-<6 years, 6 -<12 years) - SAF	SAF
14.3.8	L	Listing of treatment-emergent serious adverse events	SAF
14.3.9	L	Listing of deaths	SAF
14.3.10	L	Listing of adverse events leading to discontinuation of study medication or death	SAF
14.3.11	T	Statistics on laboratory values for each time point relative to bleeding and surgery events (2 sub-tables: Hematology, Clinical chemistry)	SAF
14.3.12	L	Abnormal laboratory value listing (2 sub-listings: Hematology, Clinical chemistry)	SAF
	T	Statistics on vital signs for each time point relative to bleeding and surgery events	SAF
14.3.13	L	Abnormal vital signs listing	SAF
14.3.14	L	Abnormal physical examination findings	SAF

*Listings will generally be sorted by age group and subject number*

16.2		Subject Data Listings (section 16.2 of the CSR)	
16.2.1.1	L	Prematurely discontinued subjects (inc. time in study and number of EDs)	All (enrolled subjects)
16.2.1.2	L	Study Completion – All enrolled subjects	All
16.2.2	L	Protocol violations and data issues flagged by “minor” and “major”	All
16.2.3	L	Disposition of subjects with respect to analysis populations	All screened subjects
16.2.4.1	L	Subject demographics – All enrolled subjects	All enrolled subjects
16.2.4.2	L	Medical history	All
16.2.4.3.1	L	Prior and concomitant medication	All
16.2.4.3.2	L	Co-medication used in the treatment of bleeding episodes	BLEED, BLEED-PP
16.2.4.3.3	L	Concomitant medication during surgery	Surg, Surg-PP
16.2.5.1	L	Octafibrin doses during study including reason for treatment	All
16.2.5.2	L	Deviations from the planned schedule of PK assessments	All
16.2.5.3	L	FIX concentrations (IU/mL) per assay during PK profile and recovery determination	All

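### SAP 10 and Table 14.3.7 start the younger age stratum at 2 years although entry has no minimum age, and the SAP 10.5 surgical failure rule names a FIX product where a fibrinogen product must be meant

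*SAP*

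**What the plan says.** **Age.** Protocol 4.2 admits children "Aged <12 years (at the start of treatment") and neither it nor the exclusion list in 4.3 sets a minimum. The recruitment quota for treated bleeds in Protocol 4.1 is that "at least 3 should be aged between 0 and <6 years and 3 should be aged between 6 and <12 years", and SAP 5.2 repeats it. Protocol 9.2.10 uses the same two groups as subpopulations, as does SAP 6.1: "Age 0 to <6 years versus 6 to <12 years (subpopulations of the BLEED-PP and the SURG-PP analysis set"). SAP 7.7 has no lower bound either: "Subgroup analyses are planned for the two age strata (age groups < 6 years" and 6 to 12 years).

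Two places differ. SAP 10 says that "all results will be presented stratified by the age groups (2-<6 years, 6-12 years), if appropriate, and in total", and the safety output list has "Summary of adverse events by age group (2-<6 years, 6 -<12 years) - SAF". SAP 10 also fixes each child's stratum by age at screening for all analyses.

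**Surgery.** SAP 10.5 states: "Subjects who switch to another FIX product during a surgery will be considered treatment failures". Each efficacy rating made after the switch is then imputed as None. Protocol 3.2 and 4.8 let the investigator turn to a different licensed fibrinogen concentrate, or to standard of care, when the study product is judged inadequate. The matching rule for bleeds in SAP 10.1 names cryoprecipitate and other fibrinogen-containing concentrates, and exempts receipt documented as unrelated to efficacy. Protocol 9.3.2.5 has no switch rule for surgery.

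**The concern.** Both sentences are operative analysis rules, and as written each misses cases it should cover.

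If a programmer follows SAP 10, a child under 2 counts toward the quota and the total but belongs to neither stratum. Because the stratum is set at screening, turning 2 during the study does not help. The by-age efficacy and adverse-event tables would then describe a different group from the 0 to <6 subpopulation planned in the protocol.

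If the surgical rule is applied as written, it is never triggered by another fibrinogen product. The same event is set to None for a bleed under SAP 10.1 but has no automatic consequence for a surgery. With a minimum of 2 surgeries, one such case is half of the planned minimum.

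**Working it through.** The documents give no sample size or power figure that bears on this, so the check is a comparison of texts.

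**Step 1: age definitions side by side.**

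| Place | Younger group | Older group |
|---|---|---|
| Protocol 4.2 (entry) | no minimum | under 12 |
| Protocol 4.1 (quota) | 0 to <6 | 6 to <12 |
| Protocol 9.2.10 | 0 to <6 | 6 to <12 |
| SAP 5.2 | 0 to <6 | 6 to <12 |
| SAP 6.1 | 0 to <6 | 6 to <12 |
| SAP 7.7 | <6 | 6 to 12 |
| SAP 10 | **2 to <6** | 6 to 12 |
| SAP Table 14.3.7 | **2 to <6** | 6 to <12 |

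Only the last two rows leave ages 0 to <2 without a group. The difference between 12 and <12 has no effect, because entry is under 12 and the stratum is fixed at screening.

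**Step 2: how many children.** The documents do not say how many will be under 2. Let k be that number among the minimum 3 younger bleeders, with k from 0 to 3. A literal 2 to <6 stratum then holds 3 − k children: 3, 2, 1 or 0. The total of 3 + 3 = 6 first bleeds does not change.

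**Step 3: is FIX a template remnant?** The disease is fibrinogen deficiency, yet FIX also stands where fibrinogen must be meant in SAP 7.5 (missing levels), SAP 9 (dose units) and Listing 16.2.5.6 (surgical plasma levels). So the wording in SAP 10.5 is a carry-over and not a deliberate restriction.

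**Step 4: what catches a fibrinogen switch if the rule does not.**
- Intra-operative None (SAP 4.3.6) needs uncontrolled haemostasis that forces a change of replacement regimen.
- Post-operative None needs extensive uncontrolled bleeding together with an alternate concentrate.
- The adjudication committee reviews every surgery, and its rating prevails over the investigator's.
- SAP 6.2 lists fibrinogen therapy other than the study product as a major deviation, except for emergency reasons.

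**Step 5: a case that passes through.** Another fibrinogen product is given during the operation, blood loss exceeds the expected maximum, but haemostasis is controlled. The surgeon can rate Moderate and the haematologist later Excellent. The algorithm in SAP 4.3.6 maps Moderate/Excellent to Success. Nothing in the written rules obliges the committee to change it.

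**Step 6: what the rule would do with the right product name.** Both ratings in Step 5 follow the switch, so both would be imputed as None. None/None is Failure in the algorithm, provided imputed ratings enter it. If the switch came after an Excellent intra-operative rating, the pair would be Excellent/None, which goes to primary adjudication. That does not fit the rule's own statement that such subjects are failures. The SAP does not explain how the imputation and the adjudicated ratings fit together.

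**The case against.** Much of the case on the other side stands.

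- SAP 6.1 and 7.7 already give the right lower bound, and 7.7 covers bleeds, surgeries and adverse events, the same outputs. A careful programmer would probably use it. This makes the contradiction easy to settle but does not remove it, since SAP 10 claims all efficacy results and Table 14.3.7 carries its own label.
- With about 3 children per stratum, SAP 7 and 14 allow listings to replace tables, and a listing keeps the child.
- A statistician would read FIX as fibrinogen. That is likely, but the failure rule should not depend on it.
- The case in Step 5 is narrow. An efficacy-driven switch will often meet the definition of None, and a non-emergency one is disclosed as a major deviation.

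Stronger readings are tempting but not supported. A reader might infer that by-age confidence intervals would widen sharply as children drop out of the stratum. However, the output "Statistics on successfully treated first bleeding episodes (two-sided 95% Clopper-Pearson confidence interval") is not marked for display by age group. A reader might also count the Success cells of the algorithm and conclude that all of them would turn to Failure after an intra-operative switch. SAP 4.3.6 and 10.5 name the adjudicated ratings as the algorithm's input and do not say that imputed ratings enter it, so that count rests on an assumption.

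**Conclusion.** The point holds in limited form: two wording errors in analysis rules, both worth correcting.

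Age: a literal 2 to <6 label leaves an eligible child under 2 without a stratum in the by-age efficacy and adverse-event tables. The size depends on how many such children enrol, which is unknown; it ranges from none to all 3 of the minimum 3 younger bleeders. It would be wrong to infer any effect on the primary estimate, the totals or the listings.

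Surgery: read literally, the failure rule never reaches the switch that the protocol allows. Existing safeguards catch or disclose most such switches, but a Moderate/Excellent case could stand as Success. No planned surgical success rate or interval changes, because SAP 14 plans surgical efficacy as a listing. SAP 10.5 would permit a frequency table, but none is in the output list. The effect is nil if the raters or the committee already score the switch as None.

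**What to change.** **Age.** Write 0 to <6 years and 6 to <12 years in SAP 10 and in the title of Table 14.3.7. Changing the upper bound in SAP 7.7 to <12 is editorial only.

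**Surgery.** In SAP 10.5:
1. Replace the trigger with receipt of cryoprecipitate, or of a fibrinogen-containing concentrate other than the study product, after the first study infusion for that surgery and before the efficacy assessment in question. The window matters: without it, product given before the surgery could count.
2. Keep the imputation of None for each later assessment.
3. State before database lock how this imputation relates to the adjudicated ratings that enter the algorithm, including what happens to an Excellent/None pair.

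The SAP 10.1 exemption for receipt documented as unrelated to efficacy is absent from SAP 10.5. Adding it is a separate choice for the sponsor. It would relax the present rule and should be described that way.

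**Cost.** SAP text only, with no new data and no protocol change. The age edit corrects labels. The surgical edit affects a secondary endpoint: an efficacy-related switch not already rated None could move from Success to Failure or to adjudication. With so few surgeries, settling it before lock avoids a choice made knowing which case it changes.

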### 10.1 Treatment of first bleeding episode

The first bleeding episode covers the time period from the first *Octafibrin* infusion until 24 hours (i.e., 1 day) after the last infusion or the end of the treatment observation period, whichever comes last

Haemostatic efficacy will be displayed by covariates (sex, age groups, weight, and type of bleeding) in tables or with covariates in listings depending on the number per subgroup.

The following will be presented following the manners of presentation described in section 7:

- Number of subjects with at least one bleeding episode
- Type of first bleeding episode (spontaneous, traumatic, post-operative, other)
- Site of first bleeding episode
- The duration of the first bleeding episode will be calculated.  
If the end time of a bleeding episode is missing it will be set to 23:59 of the same day, if the start time of a bleeding episode is missing it will be set to 0:00 of the same day.
- Severity of the first bleeding episodes (mild, moderate, severe)
- Efficacy assessment of the treatment made by the investigator (excellent, good, moderate, none) for the first bleeding episode.

For the following subjects, the haemostatic efficacy outcome will be set to the worst efficacy category, i.e., 'none':

- Subjects who withdraw from the study due to lack of efficacy during or after the first bleeding episode
- Subjects receiving cryoprecipitate or concentrates containing fibrinogen other than the IMP between first infusion and efficacy assessment for the first bleeding episode (unless it is clearly documented that these products were administered for reasons unrelated to IMP efficacy [e.g., pharmacy error])
- Subjects with missing haemostatic efficacy assessment after the first bleeding episode
- In addition to the four points scale the proportion of first bleeding episodes successfully treated with *Octafibrin* will be evaluated. "Successfully treated" are all "excellent" and "good" efficacy ratings of treated bleeding episodes. A two-sided 95% CI for the success rate in haemostatic efficacy ('excellent' or 'good') according to Clopper/Pearson will be computed.
- Treatment details: number of exposure days, number of injections, dosing incl. batch numbers., consumption of *Octafibrin* (IU/kg) for the first bleeding episode will be listed

- Any haemostatic co-medication will be listed.

### 10.2 Clot strength (MCF)

MCF and fibrinogen activity will be measured for each bleeding episode, once pre-infusion and once 1 hour after the first infusion. The analysis of MCF will be provided for the BLEED population.

The following will be presented following the manners of presentation described in section 7:

- Descriptive statistics of MCF and fibrinogen activity before and 1 hour after the end of the first infusion over all bleeding episodes, as well as changes between the two time points will be presented, together with 2-sided 95% CIs based on the paired t-test for the difference.
- If the number of bleedings is appropriate an analysis as described before will be provided separated by the 4-point haemostatic efficacy scale (excellent, good, moderate, none) and/or a dichotomised haemostatic efficacy scale (excellent/good, moderate/none). Otherwise listings with the patient data for MCF and fibrinogen activity will be given.
- If the number of bleedings is appropriate box plots will be provided separated by the 4-point haemostatic efficacy scale and/or the dichotomised haemostatic efficacy scale for MCF and fibrinogen activity.

### 10.3 In-vivo Recovery

IVR will be determined for the first infusion of each bleeding episode. The analysis population will be the BLEED population.

Incremental IVR (response) will be calculated as the increase in plasma fibrinogen (i.e., Clauss data) between the pre-infusion and the maximum of the 1-hour and 3-hour post-infusion measurement (expressed as absolute concentration in plasma [mg/dL]), divided by the exact dose of *Octafibrin* per body weight ([mg/kg]):

$$\text{Incremental IVR (response)} = \text{IVR} \left( \frac{\text{mg/dL}}{\text{mg/kg}} \right) = \frac{\Delta \text{value} \left( \frac{\text{mg}}{\text{dL}} \right)}{\text{dose (mg)/body weight(kg)}}$$

Classical IVR will be calculated as the increase in plasma fibrinogen (i.e., Clauss data) between the pre-infusion and the maximum of the 1-hour and 3-hour post-infusion measurement (expressed as absolute concentration in plasma [mg/mL]) multiplied with the plasma volume (mL, calculated according to the formula below), divided by the exact dose of *Octafibrin* (mg) (see also formula described by Nadler [2]):

Classical IVR (%) = 100% x actual/expected increase =

100% x maximum increase in fibrinogen plasma level 1-hour and 3-hour post-infusion compared to pre-infusion [mg/dL] x plasma volume (dL)  
divided by  
exact dose of component in IMP administered [mg]:

$$\text{classic IVR (\%)} = \frac{100 \times \Delta \text{value} \left( \frac{\text{mg}}{\text{dL}} \right) \times \text{plasma volume (dL)}}{\text{exact dose (mg)}}$$

The formula for the calculation of the plasma volume is:

plasma volume (mL) = (1-hematocrit at pre-infusion (1)) x blood volume (mL)

with

blood volume (mL) = ((366.9 x (height in m)) + (32.19 x body weight in kg) + 640.1  
for males and

blood volume (mL) = ((356.1 x height in m)) + (33.08 x body weight in kg) + 183.3  
for females

If the number of bleedings is sufficient to be separated into minor and major bleedings descriptive statistics will be generated to show the distribution of IVRs separated by minor and major bleeding events.

Fibrinogen levels documented before, 1 hour and 3 hours after each infusion will be listed.

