Patients should be treated with the investigational medicinal product (IMP) whenever possible. If, in the opinion of the investigator, a bleeding episode is not effectively stopped or surgical prophylaxis is not adequate after the recommended dose of *Octafibrin* has been administered, the subject may receive a different licensed fibrinogen concentrate (e.g., Haemocomplettan P®/RiaSTAP™) or whatever the investigator considers standard of care. The use of another licensed fibrinogen concentrate is also permitted in emergency situations, e.g., if the IMP is not available for the patient in time.

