### 9.3.2.3 *In-vivo recovery*

IVR will be determined for the first infusion of each bleeding episode (see Section 7.2.2.3). The analysis population will be the BLEED population.

**Incremental IVR (response)** will be calculated as the maximum increase in plasma fibrinogen (i.e., Clauss data) between the pre-infusion and the 3-hour post-infusion measurement (expressed as absolute concentration in plasma [mg/dL]), divided by the exact dose of *Octafibrin* (expressed as mg/kg dosed):

Incremental IVR (response) (mg/dL increase/[mg/kg b.w.]) =

Maximum increase in fibrinogen plasma level up to the 3-hour measurement post-infusion compared to pre-infusion (mg/dL) /  
(exact dose of component in IMP administered [mg]/b.w. [kg])

**Classical IVR** will be calculated as the maximum increase in plasma fibrinogen (i.e., Clauss data) between the pre-infusion and the 3-hour post-infusion measurement (expressed as absolute concentration in plasma [mg/dL]), divided by the total dose of *Octafibrin* per expected plasma volume (expressed as mg/dL, expected plasma volume being estimated based on the blood volume formula described by Nadler [27]):

Classical IVR (%) =

100% x actual/expected increase =

100% x maximum increase in fibrinogen plasma level 1 and 3 hours post-infusion compared to pre-infusion (mg/dL) x plasma volume (dL) / (exact dose of component in IMP administered [mg]).

Descriptive tables will show the distribution of IVRs separated by minor and major bleeding events. Fibrinogen levels before and 1 hour after each infusion will be listed.

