  - Bleeding disorder other than congenital fibrinogen deficiency
  - End-stage liver disease (i.e., Child-Pugh-score B or C)
  - Suspicion of an anti-fibrinogen inhibitor as indicated by previous IVR, if available  $<0.5$  (mg/dL)/(mg/kg)

- Treatment with any fibrinogen concentrate or other fibrinogen-containing blood product within 2 weeks prior to start of treatment for the bleeding episode.
- Did not use any coagulation-active drug (i.e., non-steroidal anti-inflammatory drugs, warfarin, coumarin derivatives, platelet aggregation inhibitors) within 1 week prior to start of treatment for the first bleeding episode, or as a planned or expected medication during the time period from Day 1 until 24 hours (i.e., 1 day) after the last *Octafibrin* infusion

Bleeding analysis set (BLEED): all documented bleeding episodes treated with *Octafibrin* in subjects of the FAS.

Bleeding per protocol analysis set (BLEED-PP): all documented bleeding episodes with no major protocol deviations, i.e. fulfilling the following conditions:

- Fully documented haemostatic efficacy data available for the bleeding
- $\geq 90\%$  of the planned total dose of the IMP was given for the bleeding
- $\geq 80\%$  of the calculated dose (if no dose was calculated, 0% will be assumed) of the IMP was given over all further infusions of the bleeding according to the treatment schedule
- The patient with the respective bleeding did not meet any of the following exclusion criteria:
  - Bleeding disorder other than congenital fibrinogen deficiency
  - End-stage liver disease (i.e., Child-Pugh-score B or C)
  - Suspicion of an anti-fibrinogen inhibitor as indicated by previous IVR, if available  $<0.5 \text{ (mg/dL)/(mg/kg)}$
  - Treatment with any fibrinogen concentrate or other fibrinogen-containing blood product within 2 weeks prior to start of treatment for the bleeding episode.
- The patient with the respective bleeding did not use any coagulation-active drug (i.e., non-steroidal anti-inflammatory drugs, warfarin, coumarin derivatives, platelet aggregation inhibitors) within 1 week prior to start of treatment for the first bleeding episode, or as a planned or expected medication during the time period from Day 1 until 24 hours (i.e., 1 day) after the last *Octafibrin* infusion

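### First-infusion IVR has no rule for another fibrinogen product given before the 3-hour sample, and taking the 1-h/3-h maximum selects the contaminated value

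*SAP*

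**What the plan says.** **How IVR is built.** SAP 10.3 takes the "increase in plasma fibrinogen (i.e., Clauss data) between the pre-infusion and the maximum of the 1-hour and 3-hour post-infusion measurement" and divides it by the exact Octafibrin dose per kg. Classical IVR uses the same numerator. Protocol 9.3.2.3 likewise uses the "Maximum increase in fibrinogen plasma level up to the 3-hour measurement post-infusion compared to pre-infusion (mg/dL").

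**Where it is applied.** SAP 10.3 states: "IVR will be determined for the first infusion of each bleeding episode. The analysis population will be the BLEED population". SAP 6.1 defines that set broadly: "Bleeding analysis set (BLEED): all documented bleeding episodes treated with" Octafibrin in FAS subjects. Bleeds in which another product was used stay in.

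**What may be given.** If the investigator judges that a bleed has not been effectively stopped after the recommended dose, "the subject may receive a different licensed fibrinogen concentrate" or other standard of care (Protocol 3.2; also 4.4.1 and 4.8). No minimum interval is stated.

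**What is done about it.** Protocol 9.3.1 and SAP 10.1 and 10.4 set the haemostatic rating to the worst category when cryoprecipitate or another fibrinogen concentrate is given before the assessment, unless the reason is documented as unrelated to efficacy. None of these sections mentions IVR, MCF or fibrinogen levels. Protocol 9.6 says missing IVR and MCF values are not replaced, which does not cover values that are present but contaminated.

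**MCF.** Under SAP 10.2, "MCF and fibrinogen activity will be measured for each bleeding episode, once pre-infusion and once 1 hour after the first infusion". It too is analysed in all treated bleeds.

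**The concern.** The numerator counts all fibrinogen in plasma at the sampling time, whatever its source. The denominator counts only Octafibrin. The ratio measures response to Octafibrin only if nothing else supplied fibrinogen between the pre-infusion sample and the sample used.

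The maximum makes the error one-sided. If another product raises the 3-h level above the 1-h level, the formula discards the valid 1-h sample and keeps the invalid 3-h one.

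Response by incremental IVR is a named secondary objective, and as few as six children may contribute bleeds, so one distorted value can move the reported mean. The event itself was foreseen, since the rating has a rule for it. The PK phase also has a safeguard: PK-PP excludes patients whose concomitant medication may confound results (Protocol 9.2.4). Recovery in bleeds has neither.

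**Working it through.** The documents give no expected IVR for this trial and no sample-size calculation, so there is no planned figure to reproduce. The check applies the SAP formula to an illustrative bleed.

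**Inputs from the documents**
- Median incremental IVR from FORMA-01: 1.77 (mg/dL)/(mg/kg) (SAP 5.1)
- Target levels: 100 mg/dL minor, 150 mg/dL major (Protocol 5.4.3)
- Fibrinogen half-life: 3-5 days (Protocol 1.1)
- Minimum number of patients with an assessed bleed: 6 (Protocol 9.1)

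**Assumptions, not in the documents**
- Baseline fibrinogen 0 and true IVR 1.77
- The other product adds 50-100 mg/dL before the 3-h sample

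**Step 1: first dose** = target / 1.77
- Minor: 100 / 1.77 = 56.5 mg/kg
- Major: 150 / 1.77 = 84.7 mg/kg

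**Step 2: IVR under the SAP formula** = (target + added rise) / first dose, ignoring decay
- Minor: 150 / 56.5 = 2.66 to 200 / 56.5 = 3.54, i.e. 1.5 to 2.0 times the true 1.77
- Major: 200 / 84.7 = 2.36 to 250 / 84.7 = 2.95, i.e. 1.33 to 1.67 times

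**Step 3: effect on a group of six**, five bleeds at 1.77 and one affected
- Lowest: (5 × 1.77 + 2.36) / 6 = 1.87, +6%
- Highest: (5 × 1.77 + 3.54) / 6 = 2.065, +17%
- Median: 1.77 in both cases

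With one affected bleed among twelve, a doubled value raises the mean to (11 × 1.77 + 3.54) / 12 = 1.92, +8%.

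**Step 4: does the maximum pick the contaminated sample?** Between 1 h and 3 h, natural decay is 1 − 2^(−2/72) = 1.9% at a 3-day half-life and 1 − 2^(−2/120) = 1.1% at 5 days. A net contribution above about 2% of the 1-h level is therefore enough for the 3-h value to be chosen.

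**Step 5: cross-check with decay.** Here the other product is assumed to be 20 mg/kg, 40 mg/kg or a repeat of the first dose, about 2 h after the first infusion, with response 1.77. These amounts only drive the arithmetic. With k = ln 2 / half-life, first dose D, second dose D2 and true IVR r:
- C1h = r·D·exp(−k)
- C3h = r·D·exp(−3k) + 1.77·D2·exp(−k)
- SAP IVR = max(C1h, C3h) / D

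Example (minor, D2 = 40, half-life 72 h): C1h = 99.0 and C3h = 97.1 + 70.1 = 167.3. The SAP formula gives 167.3 / 56.5 = 2.96, against 99.0 / 56.5 = 1.75 from the clean sample.

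| Target | True IVR | Clean 1-h IVR | SAP IVR |
|---|---|---|---|
| 100 | 1.77 | 1.75-1.76 | 2.34-3.50 |
| 150 | 1.77 | 1.75-1.76 | 2.13-3.50 |
| 100 | 20% lower | 1.40-1.41 | 2.00-3.15 |
| 150 | 20% lower | 1.40-1.41 | 1.79-3.15 |

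Across this grid the SAP value is about 1.2-2.2 times the clean value. In the last two rows a recovery below 1.77 is reported as one above it.

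**Step 6: timing.**

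| Other product given | IVR | 1-h MCF and fibrinogen |
|---|---|---|
| Before the 1-h sample | Both samples affected | Affected |
| Between the 1-h and 3-h samples | Maximum selects the affected 3-h value | Not affected |
| After the 3-h sample | No effect | No effect |

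**The case against.** The strongest reply is that the event may never happen, and that the plan would reveal it if it did. Bias needs another product within about 3 h of the first infusion. Fibrinogen levels before, 1 h and 3 h after each infusion are listed (SAP 10.3), as is haemostatic co-medication (SAP 10.1 and 10.4). The median is reported beside the mean (SAP 7.1). BLEED contains repeat bleeds, so there may be more than six values to dilute one outlier. A separate recovery estimate comes from the PK phase in PK-PP. Everything is descriptive (Protocol 9), and further population exclusions can be agreed in writing before database closure (note in Protocol 9.2.9).

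This limits the consequence, but it does not close the gap. Listings let a reader find an affected bleed; they do not change the summary statistic. A decision made late in an open-label study would be taken with the values in view. Moving to BLEED-PP would not help either: its criteria in SAP 6.1 address fibrinogen products only in the 2 weeks before treatment. SAP 6.2 lists non-study fibrinogen as a major deviation, but exempts emergency use and removes nothing from BLEED.

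A reader might infer four stronger points that the documents do not support:
- **Recovery is inflated in treatment failures generally.** It is not; later use of another product leaves both samples untouched. The protocol states no minimum delay, which is not the same as expressly providing for use at every moment.
- **A second Octafibrin infusion inflates it too.** Additional infusions are decided on levels from subsequent study days (Protocol 5.4.3 and 6.1.3.2), after the Day 1 3-h sample. The requirement of at least one infusion on Day 1 leaves an earlier one possible but unscheduled, and a second infusion is not in itself a failure.
- **Octafibrin will look best where it worked least.** No IVR-by-outcome output is planned; IVR is split only by minor and major bleeding.
- **MCF in the worst outcome group reflects the other product.** MCF is one 1-h sample, not a maximum, and the split by outcome is made only if numbers allow. That group also holds missing assessments and bleeds rated in that category on the scale itself.

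**Conclusion.** The point holds in conditional form. As written, the IVR rule credits Octafibrin with fibrinogen from another product given before the 3-h sample, and it prefers that sample to a clean 1-h one. The 1-h MCF and fibrinogen values share the problem only if the product is given before the 1-h sample.

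Under the stated assumptions the affected bleed's IVR is about 1.3-2.0 times too high, and one such bleed among six raises the mean by 6-17% with the median unchanged. The 50-100 mg/dL rise and its timing are assumed; the documents give no rate or size for such use. If none occurs within 3 h, the effect is zero.

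The primary endpoint is untouched. This is a defect in a descriptive secondary analysis, worth correcting because the correction is specific and cheap.

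**What to change.** Add to SAP 10.2 and 10.3, as an analysis rule only, with no change to what may be given to patients:

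- For IVR (incremental and classical), 1-h MCF and 1-h fibrinogen, use only post-infusion samples taken before any further fibrinogen-containing product (other concentrate, cryoprecipitate, plasma) or any further study infusion. The study-infusion clause is a precaution, since none is scheduled in that window.
- If only the 1-h sample qualifies, base IVR on it. If no sample qualifies, set the value to missing.
- List and flag the excluded samples, and report the number of affected bleeds.

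**Cost.** One paragraph in the SAP and an occasional missing value. Missing values would arise in bleeds that were not stopped early, so the count should appear beside the IVR summary. The rule needs clock times. Octafibrin infusion times (Protocol 5.8) and actual sampling times (Protocol 7.3.1) are recorded, but for other concentrates Protocol 4.4.1 asks only for details. Confirm that the CRF captures the clock time of these products, and add the field if it does not.
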